8.2 Laboratory Evaluations

8.2.1 Clinical Laboratory Evaluations

A total of 2 mL blood will be collected for screening clinical labs for the evaluation of eligibility. If screening laboratory results are out of range value, they may be repeated once provided there is an alternative explanation for the out of range value. Participants must have acceptable screening laboratory findings within 7 days prior to enrollment. The acceptable ranges for study eligibility are listed in [Appendix B](#).

For the assessment of safety, a total of 2 mL of blood will be collected for clinical safety labs on visit 7, about 4 weeks after the third dose of vaccine. These include a CBC with differential for WBC, Hg, ANC, Platelet count, creatinine, albumin, and ALT. In addition, 2 mL of blood will be collected at visit 6 (7-days post-third dose of vaccine) for ALT, serum bilirubin, and creatinine. The grading of toxicity for clinical safety lab values that are not in the normal range is

provided in [Appendix C](#).

All women will have a urine pregnancy test performed during screening and a urine pregnancy test on the vaccination days. The results of the urine pregnancy test must be negative prior to enrollment in the study, and prior to each vaccination.

For those laboratory tests run as part of a panel of tests, but not required by the protocol, the site is required to do the following:

- Enter all non-required lab results into the database in the comments section of the eCRF.
- When a result is abnormal per the site normal laboratory reference range, the result must be:
 - Entered in the comments section of the database including assessment for clinical significance by site PI,
 - An AE generated and followed until resolution if clinically significant based on assessment by the site PI,
 - If clinically significant, graded according to either the toxicity tables in [Appendix C](#) or if a grading scale is not available, the PI should use the guidance for AE grading.

8.2.2 Clinical Microbiology Evaluation

For any participant who experiences any diarrhea within 3 days (72 hours) of receipt of any dose of study product will be requested to provide a stool specimen for stool culture.

For any participant (irrespective of the route of administration) that experiences moderate or severe diarrhea within 28 days of receipt of any dose of study product will be requested to provide a stool specimen for stool culture. If the participant experiences further episodes of moderate or severe diarrhea, there will be a maximum of one stool culture to be performed per 7 day period.

Upon notification of eligible diarrhea, study staff will instruct participants to come to the research clinic to collect a stool specimen or a study staff member will go to the household of the participant for the collection of a stool specimen. The stool will be cultured, using standard bacteriological methods, for the presence of: ETEC, *Vibrio cholerae*, *Shigella* sp., *Salmonella* sp., and *Campylobacter* sp.

8.2.3 Special Assays or Procedures

Detailed procedures for the conduct of each of the immunology assays are described in the *Manual of Procedures*.

The following immunology assays will be performed at icddr,b (Dhaka, Bangladesh):

Table 3: Assays to be performed at icddr,b

Immunology Assay:	Visit(s) collected at:
Serum anti-dmLT IgG and IgA by ELISA	Visits 1, 2, 3, 4, 5, 6, 7, and 8
dmLT-specific IgG and IgA ASC assays	Visits 1, 2, 3, 4, 5, and 6
dmLT-specific IgG and IgA ALS assays	Visits 1, 2, 3, 4, 5, and 6
ASC homing studies	Visits 2, 4, and 6
Fecal total IgA and anti-dmLT IgA by ELISA	Visits 1, 2, 3, 4, 5, 6 and 7
Saliva total IgA and anti-dmLT IgA by ELISA	Visits 1, 2, 3, 4, 5, 6 and 7
dmLT-specific memory B cell responses	Visits 1, 4, 6, 7, 8, and 9

The following immunology assay will be performed at CVD (Baltimore, MD, U.S.):

- Serum toxin (LT) neutralization assay
- dmLT-specific effector and memory T cell responses, by CyTOF--including the characterization of: homing potential, cytokine/chemokine production profile, degranulation capacity, and activation potential
 - Collected at visits screening, 4, 6, 7, 8, and 9

8.2.4 Specimen Preparation, Handling, and Shipping

All sample collection time are described in the [Table 3](#) and [Appendix A](#).

8.2.4.1 Instructions for Specimen Preparation, Handling, and Storage

Instructions for specimen preparation, handling, and storage are described in the *Manual of Procedures*.

8.2.4.2 Specimen Shipment

Instructions for specimen shipping are described in the *Manual of Procedures*.

9 ASSESSMENT OF SAFETY

9.1 Specification of Safety Parameters

The Investigator is responsible for reporting all AEs that are observed or reported during the study, regardless of their relationship to investigational product or their clinical significance.

All events will be recorded on appropriate clinical report forms with notation of duration, severity, and outcome.

Safety and tolerability will be assessed by the frequency and severity of:

1. Study vaccine-related SAEs occurring from first vaccination through 6 months after the last study vaccination.
2. Solicited AEs – reactogenicity events occurring within 7 days of each dose of vaccine:
 - a. Systemic Reactions to include: feverishness (chills/shivering/sweating), fatigue (tiredness), malaise (general unwell feeling), myalgia (body aches, muscular pain), or headache, diarrhea, nausea, vomiting, or abdominal discomfort. Note: for the oral and SL routes of administration, diarrhea, nausea, vomiting, and abdominal discomfort will be evaluated as local reactions as described below.
 - b. Systemic Reactions to also include the measurement of daily oral temperature
 - c. Local Reactions
 - i. For oral route of administration: irritation of the oral cavity or tongue, plus diarrhea, nausea, vomiting, and abdominal discomfort
 - ii. For SL route of administration: irritation of the oral cavity or tongue, or facial nerve disturbance, plus diarrhea, nausea, vomiting, and abdominal discomfort
 - iii. For ID route of administration: injection site pain, redness, swelling, bruising, itching, hypo/hyper pigmentation and induration, vesicles or hardened mass.
3. Unsolicited AEs – study vaccine-related non-serious AEs from first vaccination through 28 days after the last (third) dose of vaccine

4. Withdrawals and discontinuation of study vaccinations will be assessed as a part of determining tolerability

9.2 Methods and Timing for Assessing, Recording, and Analyzing Safety Parameters

9.2.1 Adverse Events

Adverse Event (AE): International Conference on Harmonization (ICH) E6 defines an AE as any untoward medical occurrence in a patient or clinical investigation participants administered a pharmaceutical product regardless of its causal relationship to the study treatment. An AE can therefore be any unfavorable and unintended sign (including an abnormal laboratory finding), symptom, or disease temporally associated with the use of a medicinal (investigational) product. The occurrence of an AE may come to the attention of study personnel during study visits and interviews of a study recipient presenting for medical care, or upon review by a study monitor.

AEs, including local and systemic (subjective and quantitative) reactions, not meeting the protocol-defined criteria for SAEs will be captured on the appropriate data collection form and eCRF. Information to be collected for unsolicited non-serious AEs includes event description, date of onset, licensed study physician's assessment of severity and relationship to study product and alternate etiology (if not related to study product) (assessed only by those with the training and authority to make a diagnosis and listed on the Form FDA 1572 as the site principal investigator or sub-investigator), date of resolution of the event, seriousness and outcome. AEs occurring during the collection and reporting period will be documented appropriately regardless of relationship. AEs will be followed through resolution.

Any medical condition that is present at the time that the participant is screened will be considered as baseline and not reported as an AE. However, if the severity of any pre-existing medical condition increases, it will be recorded as an AE.

AEs must be graded for severity and assessed for relationship to study product (see definitions below). Adverse events characterized as intermittent require documentation of onset and duration of each episode. The start and stop date of each reported AE will be recorded on the appropriate data collection form and eCRF.

FDA defines an AE as any untoward medical occurrence associated with the use of a drug in humans, whether or not considered drug related.

Severity of Event: AEs will be assessed by a licensed study physician listed on the Form FDA 1572 as the site principal investigator or appropriate sub-investigator the "Laboratory and

Clinical Toxicity Grading Scales” in [Appendix C](#). For events not included in the protocol-defined grading system, the following guidelines will be used to quantify severity:

- Mild (Grade 1): Events require minimal or no treatment and do not interfere with the participant’s daily activities.
- Moderate (Grade 2): Events result in a low level of inconvenience or concern with therapeutic measures. Moderate events may cause some interference with functioning and daily activities.
- Severe (Grade 3): Events interrupt the participant’s usual daily activities and may require systemic drug therapy or other treatment. Severe events are usually incapacitating.

Relationship to Study Product: The study physician’s assessment of an AE’s relationship to study product is part of the documentation process, but it is not a factor in determining what is or is not reported in this study. If there is any doubt as to whether a clinical observation is an AE, the event should be reported. The relationship to study product must be assessed for AEs using the terms: related or not related. In a clinical trial, the study product must always be suspect. To help assess, the following guidelines are used:

- Related – There is a reasonable possibility that the study product caused the adverse event. Reasonable possibility means that there is evidence to suggest a causal relationship between the study product and the adverse event.
- Not Related – There is not a reasonable possibility that the administration of the study product caused the event.

9.2.2 **Solicited Events**

The Toxicity Grading Scales to be used to guide the grading of solicited AEs is in [Appendix C](#).

9.2.3 **Serious Adverse Events**

Serious Adverse Event (SAE): An adverse event or suspected adverse reaction is considered “serious” if, in the view of either the site principal investigator or sponsor, it results in any of the following outcomes:

- Death,
- a life-threatening adverse event*,
- inpatient hospitalization (defined by local practice as the study participant being present in the hospital greater than 24 hours) or prolongation of existing hospitalization,

- a persistent or significant incapacity or substantial disruption of the ability to conduct normal life functions, or
- a congenital anomaly/birth defect.
- Important medical events that may not result in death, be life-threatening, or require hospitalizations may be considered serious when, based upon appropriate medical judgment they may jeopardize the patient or participant and may require medical or surgical intervention to prevent one of the outcomes listed in this definition. Examples of such medical events include allergic bronchospasm requiring intensive treatment in an emergency room or at home, blood dyscrasias or convulsions that do not result in inpatient hospitalization, or the development of drug dependency or drug abuse.

** Life-threatening adverse event. An adverse event is considered “life-threatening” if, in the view of either the site principal investigator or sponsor, its occurrence places the patient or participant at immediate risk of death. It does not include an adverse event that, had it occurred in a more severe form, might have caused death.*

SAEs will be:

- Assessed for severity and relationship to study product and alternate etiology (if not related to study product) by a licensed study physician listed on the Form FDA 1572 as the site principal investigator or sub-investigator.
- Recorded on the appropriate SAE forms and the eCRF.
- Followed through resolution by a licensed study physician listed on the Form FDA 1572 as the site principal investigator or sub-investigator.
- Reviewed and evaluated by an Independent Safety Monitor (ISM), Independent Protocol Safety Team (IPST), both the DMID DSMB and local DSMB (periodic review unless related), DMID, and the IRB.

9.2.4 Procedures to be followed in the Event of Abnormal Laboratory Test Values or Abnormal Clinical Findings

The site principal investigator or appropriate sub-investigator is responsible for recording all AE/SAEs that are observed or reported during this study, regardless of the relationship to study product. AE/SAEs or abnormal clinical findings will be collected, assessed, documented, reported, and followed until resolved or considered stable.

9.3 Reporting Procedures

9.3.1 Serious Adverse Events

If in the opinion of a study physician Investigator the event meets the criteria of a SAE, the following procedures will occur:

All SAEs will be:

- recorded on the appropriate AE eCRF, DMID SAE form, and icddr,b SAE form
- followed by a study physician until satisfactory resolution or until the PI or co-Investigator deems the event to be chronic or the participant to be stable as reviewed by a study physician

Any AE that meets a protocol-defined serious criterion must be submitted immediately (within 24 hours of site awareness) on the DMID SAE form to the DMID Pharmacovigilance Group at the following address:

DMID Pharmacovigilance Group
Clinical Research Operations and Management Support (CROMS)
[name] [name] 650
[name], USA
SAE Hot Line: [name] (US) or [name] (outside US)
SAE [contact] (US) or [name] (outside US)
SAE Email Address: [contact]

In addition to the SAE form, selected SAE data fields must also be entered into Advantage eClinicalSM. Please see the protocol-specific MOP for details regarding this procedure.

Other supporting documentation of the event may be requested by the DMID Pharmacovigilance Group and should be provided as soon as possible.

The site will send a copy of the SAE report(s) to the ISM when they are provided to the DMID Pharmacovigilance Group. The DMID Medical Monitor and DMID Clinical Project Manager will be notified of the SAE by the DMID Pharmacovigilance Group. The DMID Medical Monitor will review and assess the SAE for regulatory reporting and potential impact on study participant safety and protocol conduct.

At any time after completion of this study, if the site principal investigator or appropriate sub-investigator becomes aware of an SAE that is suspected to be related to study product, the site principal investigator or appropriate sub-investigator will report the event to the DMID Pharmacovigilance Group.

In addition, such events will be reported to the local IRB/ERC in accordance with IRB/ERC policy.

All SAEs will be followed until satisfactory resolution or until the PI or Co-Investigator deems the event to be chronic or the participant to be stable.

9.3.2 Regulatory Reporting for Studies Conducted Under DMID-Sponsored IND

Following notification from the investigator, DMID, the IND sponsor, will report any suspected adverse reaction that is both serious and unexpected. DMID will report an AE as a suspected adverse reaction only if there is evidence to suggest a causal relationship between the study product and the adverse event. DMID will notify FDA and all participating investigators (i.e., all investigators to whom the sponsor is providing drug under its INDs or under any investigator's IND) in an IND safety report of potential serious risks from clinical trials or any other source, as soon as possible, but in no case later than 15 calendar days after the sponsor determines that the information qualifies for reporting as specified in 21 CFR Part 312.32. DMID will also notify FDA of any unexpected fatal or life-threatening suspected adverse reaction as soon as possible but in no case later than 7 calendar days after the sponsor's initial receipt of the information. Relevant follow-up information to an IND safety report will be submitted as soon as the information is available. Upon request from FDA, DMID will submit to FDA any additional data or information that the agency deems necessary, as soon as possible, but in no case later than 15 calendar days after receiving the request. All serious events designated as "not related" to study product(s), will be reported to the FDA at least annually in a summary format.

9.3.3 Reporting of Pregnancy

Reproductive animal toxicity studies have not been conducted with dmLT vaccine. Therefore, the risk to the unborn fetus or pregnant mother is unknown. Consequently, all women will be instructed to avoid pregnancy through the 28 days from receipt of the last dose of vaccine.

Female participants must be non-pregnant at enrollment and prior to the receipt of each dose of vaccine. *All women presenting for screening will have urine pregnancy testing. "Females of childbearing potential must agree to use an efficacious hormonal or barrier method of birth control from screening and through 28 days post last dose of vaccine. Abstinence is also acceptable."*

If an eligible female participant has a positive urine pregnancy test at any time, she will not receive any further study treatment. Should a female participant become pregnant subsequent to Dose 1, the Investigator will obtain permission from the participant to follow the participant's pregnancy. If permission is obtained, the Investigator should report to DMID the course of pregnancy including perinatal and neonatal outcome on the appropriate eCRF.

Although pregnancy is not a SAE, all pregnancies occurring during this study will be reported in the same time frame as SAEs. The Investigator will immediately notify the DMID MM and CPM about the pregnancy and complete a Pregnancy Report eCRF. If an SAE occurs during the pregnancy, the SAE will be reported on the appropriate SAE form and faxed to DMID-CROMS if appropriate.

9.4 Type and Duration of Follow-up of Subjects after Adverse Events

All AEs and SAEs will be followed until resolved or considered stable.

9.5 Halting Rules

Further dosing of any participant only for the route (oral, SL, ID) will be halted if any of the following criteria are met. The study will be halted, and all further vaccine administration will be halted for DSMB review/recommendation if any of the following criteria are met for each route of administration:

- Any participant experiences vaccine-related SAE (e.g., excluding trauma or accident) from the time of the first study vaccination through the participant's last study visit.
- Any participant experiences an injection site necrosis within 7 days of vaccination.
- Any participant experiences an anaphylactic reaction related to vaccine occurring within 24 hours after vaccination.
- Any participant experiences urticaria, laryngospasm, bronchospasm, or anaphylaxis determined to be related to vaccine and within 7 days of vaccination.
- Any participant experiences facial nerve neuropathy, within 28 days of vaccination, confirmed by an investigator and determined to be related to vaccine.
- Any participant experiences a death for any reason excluding trauma or accident.

In addition, the study will be halted if two or more participants in the same cohort or three participants across all cohorts within a route of administration (who received at least one dose of study product) experience:

- The same severe (Grade 3) study vaccine-related local solicited event,
- The same severe (Grade 3) study vaccine-related systemic solicited event,
- The same severe (Grade 3) study vaccine-related clinical laboratory test,
- The same severe (Grade 3) study vaccine-related vital sign, or
- Any other severe (Grade 3) AE of the same system organ class

Exceptions to this would be:

- If there are obvious and acceptable physiological explanation for a Grade 3 abnormality (example, grade 3 hematuria in menstruating females)

Once a halting rule is met, further dosing of the respective route will cease, but follow-up visits may continue. An *ad hoc* DMID DSMB meeting and local DSMB meeting will be convened to discuss the halting event. If, following review by both the DMID DSMB and local DSMB, this is deemed acceptable to restart the study, the study will resume, upon DMID's approval and authorization.

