### 6.6.3. Halting Rules

Further dosing of any participant only for the route (oral, SL, ID) would have been halted if any of the following criteria were met. The study would have been halted, and all further vaccine administration halted for DSMB review/recommendation if any of the following criteria had been met for each route of administration:

- Any participant experiences vaccine-related SAE (e.g., excluding trauma or accident) from the time of the first study vaccination through the participant's last study visit.
- Any participant experiences an injection site necrosis within 7 days of vaccination.
- Any participant experiences an anaphylactic reaction related to vaccine occurring within 24 hours after vaccination.
- Any participant experiences urticaria, laryngospasm, bronchospasm, or anaphylaxis determined to be related to vaccine and within 7 days of vaccination.
- Any participant experiences facial nerve neuropathy, within 28 days of vaccination, confirmed by an investigator and determined to be related to vaccine.
- Any participant experiences a death for any reason excluding trauma or accident.

In addition, the study would have been halted if two or more participants in the same cohort or three participants across all cohorts within a route of administration (who received at least one dose of study product) experienced:

- The same severe (Grade 3) study vaccine-related local solicited event,
- The same severe (Grade 3) study vaccine-related systemic solicited event,
- The same severe (Grade 3) study vaccine-related clinical laboratory test,
- The same severe (Grade 3) study vaccine-related vital sign, or
- Any other severe (Grade 3) AE of the same system organ class

Exceptions to this would have been:

- If there are obvious and acceptable physiological explanation for a Grade 3 abnormality (example, grade 3 hematuria in menstruating females)

If a halting rule had been met, further dosing of the respective route would have ceased, but follow-up visits would have continued. An *ad hoc* DMID DSMB meeting and local DSMB meeting would have been convened to discuss the halting event. If, following review by both the DMID DSMB and local DSMB, it had been deemed acceptable to restart the study, the study would have resumed, upon DMID's approval and authorization.

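### Protocol 9.5, repeated in the SAP, gives the same halting criteria two conflicting scopes: the affected route only, or the whole study

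*Protocol*

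**What the plan says.** Protocol 9.5 states the scope of a halt five times.

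1. The opening sentence limits it to a route: "Further dosing of any participant only for the route (oral, SL, ID) will be halted if any of the following criteria are met".
2. The second sentence, which governs the same bullet list, does not: "The study will be halted, and all further vaccine administration will be halted for DSMB review/recommendation". It ends with a qualifier: "if any of the following criteria are met for each route of administration".
3. The Grade 3 count rule counts events within a cohort or a route, but its action is study-wide: "the study will be halted if two or more participants in the same cohort or three participants across all cohorts within a route".
4. The closing paragraph, which covers any halting rule, goes back to the route: "Once a halting rule is met, further dosing of the respective route will cease, but follow-up visits may continue".
5. The restart sentence speaks of the study again. If, after review by both DSMBs, "this is deemed acceptable to restart the study, the study will resume", subject to the sponsor's approval.

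The SAP's Halting Rules section (the second of two sections numbered 6.6.3) carries the same text in the conditional. It has the route scope in "Further dosing of any participant only for the route (oral, SL, ID) would have been halted if any of the following criteria were met" and the study scope in "The study would have been halted, and all further vaccine administration halted for DSMB review/recommendation".

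**The concern.** The criteria on this list include a vaccine-related SAE, anaphylaxis, and any death not due to trauma or accident. A rule of this kind must give one answer at the moment it is triggered. Suppose an oral participant has a vaccine-related SAE. The opening sentence and closing paragraph leave sublingual and intradermal dosing untouched, whereas the second sentence stops it.

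The investigator, the data coordinating center and two DSMBs that function independently of each other all work from this text, and each could read it differently. At stake is whether participants in the other routes go on being dosed before the event has been reviewed. This is a question of participant safety and of consistent conduct. It does not bear on the analysis.

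**Working it through.** There is no plan figure to reproduce; the check is a comparison of texts.

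**Can any one reading satisfy every sentence of 9.5?** The possibilities turn on the qualifier about each route.

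- *Qualifier means route by route.* The opening sentence and closing paragraph fit. The second sentence's halt of all vaccine administration is then untrue, and so is the study-wide action in the Grade 3 rule.
- *Qualifier means met in every route.* The second sentence becomes a second tier above the route halt. The Grade 3 rule still halts the study on a count made within one cohort or route, while the closing paragraph stops only the respective route. An SAE or death in one route would stop that route alone, yet two matching vaccine-related Grade 3 events in one cohort would stop the study.
- *Study scope governs throughout.* The route limits in the opening sentence and closing paragraph then have no effect.

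Each reading leaves at least one operative sentence contradicted.

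**Does another section decide?**

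- Protocol 4.1 makes escalation conditional on the criteria in 9.5 and adds a criterion for progression within a route. It refers back to 9.5 and does not interpret it.
- Protocol 9.6.1 provides for an ad hoc meeting when a halting rule is met, and says what follows if the study is discontinued.
- Protocol 11.3.1 says only that meetings may become more frequent.

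None assigns some criteria to a route halt and others to a study halt, or says which sentence prevails.

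**When would the two scopes lead to different actions?** Protocol 4.1 allows one cohort to enroll at a time and bases the escalation review on data through 7 days after the third dose. Inputs from Protocol Appendix A and 9.5:

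| | Oral and sublingual | Intradermal |
|---|---|---|
| Visit 7 days after dose 3 | Day 36 | Day 50 |
| Last visit, when the SAE criterion closes | Day 209 | Day 223 |
| SAE criterion still open after that visit | 209 − 36 = 173 days | 223 − 50 = 173 days |
| First to third dose | 29 − 1 = 28 days | 43 − 1 = 42 days |

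The follow-up period is therefore long enough to contain a full dosing course in another route. The death criterion in 9.5 states no time limit at all.

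SAP section 15 shows that such overlap arose in practice. The pandemic lockdown prevented both Visit 8 of Cohort D (sublingual) and the third dose of Cohort E (intradermal), so sublingual follow-up was open while intradermal dosing was under way.

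No probability is attached to the scenario. The documents give no trigger rate, and the conflict does not depend on one.

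**The case against.** The best defense rests on the qualifier. Read as route by route, it agrees with the opening sentence, with counting within a route, and with the sentence that says what happens once any rule is met. This is a natural reading and may be what was intended. It still does not remove the explicit halt of all vaccine administration, and a reader who takes the qualifier to mean every route is not misreading the grammar.

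The second argument is that little turns on the difference, and much of it stands. Under either scope the affected route stops, both DSMBs meet, and restart needs both reviews and the sponsor's approval. Protocol 4.1 lets the sponsor stop the study at any point. The local DSMB gives a recommendation after each cohort and meets ad hoc for unexpected safety events (Protocol 9.6.3). With one cohort enrolling at a time, an event during a cohort's own dosing would normally find no other route in dosing. These provisions narrow the problem to events in follow-up; they do not remove it.

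Third, the DSMB charter mentioned in Protocol 9.6.1 may contain the missing detail. It is not among the documents, so this is possible but unverified. The protocol and SAP would still need to agree with it.

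**Conclusion.** The point holds as an internal contradiction in a safety rule. Its size is limited to whether dosing in the other routes continues while the two DSMBs review an event, mainly when follow-up in one cohort overlaps dosing in another route. That conclusion assumes the enrollment sequence in Protocol 4.1 is followed and that no document outside those reviewed fixes the scope.

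Two stronger conclusions might be inferred, and the documents support neither.

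- *Impact measured as planned headcount.* Table 1 of the Protocol plans 12 vaccinees in each of six cohorts in the other two routes, 6 × 12 = 72. That is a ceiling, reached only if the event comes before anyone in those routes is dosed. The people concerned would be unenrolled and still behind the local DSMB's recommendation. Once Cohorts A to F have finished dosing, the ceiling is 2 × 12 = 24. It also counts vaccinees only, whereas the halt covers any participant.
- *The report cannot establish whether the rule was followed, or a halt was misapplied.* The SAP describes halting only as something that would have happened, reports no dose-limiting AEs among the 40 vaccinees in Cohorts A to D who received all three doses (SAP section 5), and attributes termination to COVID-19. If no rule was met, its scope was never put to the test.

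**What to change.** Reconcile four places in Protocol 9.5: the two opening sentences with their qualifier, the Grade 3 count paragraph, the closing sentence on dosing, and the restart sentence. Each criterion should then carry one stated scope, and halt and restart should refer to the same unit. The qualifier should be reworded so that it has one meaning. The matching SAP Halting Rules text should be aligned, with any difference from the protocol in force during conduct noted in SAP section 15.

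The sponsor and the two DSMBs must choose the scope; this review takes no position on which is right. The cost is a wording change in two sections. No data collection, sample size or analysis is affected. Because the SAP records that the trial has ended, the practical value is an unambiguous account in the clinical study report and clean text for any later protocol that reuses this section.
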